### 3. Significance of this research

Despite a relative paucity of evidence for its efficacy, airway clearance therapy remains a foundational component of comprehensive CF care. Well-designed randomized controlled trials examining the efficacy of specific ACTs are generally lacking, and there are few economic pressures to drive their performance. Comparison between ACTs is also hampered by the lack of outcome measures. In this study, we will employ a highly relevant outcome measure (MCC) to characterize the effect of differing ACT modalities. Further, by collecting easily obtained molecular biomarkers (FENO and EBC nucleotide levels) that have biological relevance to the mucus clearance system and are believed to transduce physical stimuli into biological signals, and correlating them to quantitative MCC measurements, we may discover broadly useful biomarkers for research into ACT effects while also broadening our understanding of the mechanisms that control mucus clearance. These biomarkers could be used to identify ACT modalities worthy of more extensive clinical testing or to “personalize” therapies to individual patients or groups of patients with specific characteristics (e.g. mild vs. severe lung disease). We will also investigate the effects of a novel device that employs high frequency, whole body vibration, but was not developed as an ACT device, to broaden our understanding the types of mechanical stimuli that successfully increase mucus clearance. The results of this pilot can be used to inform the design of future trials of effectiveness of ACTs, including sample size, study design features, and outcome measures.

#### **4. Rationale for proposed study**

We intend to carry out this pilot study to determine the effect size (and variability) of cough alone and various ACT devices on MCC, signaling molecules, and sputum volume. We will also explore the correlation between MCC and signaling molecules, and compare a novel exercise device using whole body vibration to traditional ACT methods.

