### *Whole Body Vibration In Exercise And Therapy*

The use of whole body vibration (WBV) via a vibrating plate was developed for use in personal fitness and recreation and not as a medical therapy or intervention. These devices consist of a large plate that vibrates at frequencies generally between 20 and 70hz and with a displacement of 1-5mm. The effect of these devices is to constantly accelerate and decelerate the whole body in an oscillating manner. This acceleration is described by the simple harmonic motion equation and is proportional to the displacement of the plate and to the square of the frequency of vibration. These variables are the settings on the device. Studies of WBV in bone density and musculoskeletal outcomes in older adults did not show benefit for acceleration  $<1\ g$ , but other studies did show some benefit for WBV exerting higher magnitudes (1 to 8  $g$ ). A pilot study of WBV in individuals with cystic fibrosis showed an improvement in muscle strength and performance. These devices have not been studied as a means of airway clearance therapy, but there is anecdotal support for their use for airway clearance by individuals with CF. Furthermore, studying their effect as an ACT allows us to test the hypothesis that high energy devices, even those not specifically engineered for airway clearance such as WBV platforms, may be as effective in ACT as those devices that were specifically engineered to affect the respiratory system.

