### Randomization

[figure not shown]
Baseline (huff-cough only) measurements will be obtained at Visit 2. For visits 3-5, a single ACT method will be employed at each visit, with a randomized order in which the methods are used. We will employ a Latin-square design as shown. First, the 3 periods will be randomized, followed by the sequences (A-C). This will generate a random 3 x 3 table in which each ACT appears once in each row and column. The rows of this table will serve as a block randomization schedule, which will optimize balance for a number of subjects not divisible by the number of possible sequences. Subjects will be assigned to the next row in the table after the baseline visit (repeating the sequences every 3rd subject) to ensure eligibility prior to randomization.

[figure not shown]

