## Data analysis:

[name], biostatistician for the UNC CF Center, has been closely involved in the study design and will be responsible for overseeing the database creation and management, as well as performing final statistical computations during data analysis.

**Primary comparison:** MCC will be visualized using a whole right lung clearance vs. time plot from immediately after isotope inhalation through 274 minutes post-inhalation. The area under this curve (AUC-Clr274), will be used to reflect “total clearance”, and will serve as the primary outcome of this study. We will compare AUC-Clr274 in huff-cough alone to AUC-Clr274 measured with each of the ACT modalities (HFCWO-vest, OPEP device, and WBV device).

**Secondary comparisons:** AUC-Clr over other intervals (i.e. 94 min and 180 min), and from other lung regions of interest (i.e. peripheral and central lung zones) will be calculated and compared in similar fashion as above. Furthermore, the change in the rate of clearance (represented by the slope of the MCC curve,  $d\text{Clr}/dt$ ) before (0-16 minutes of MCC curve;  $d\text{Clr}/dt_{0-16}$ ) versus during/after the initial ACT intervention (16 – 56 minutes;  $d\text{Clr}/dt_{16-56}$ ) will be used to compare the immediate effects of each ACT versus. huff coughs alone. The mean changes in EBC purines concentrations and FeNO, (before vs. after ACT) will be calculated. If these are found to be different from zero, a comparison between huff-cough alone and each of the ACT modalities will be made. Total sputum weights and % solids at baseline and after each ACT 40 minute period will be compared across each of the ACT modalities. We will also assess for a relationship between changes in EBC measurements, FeNO, and changes in MCC.

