Means, standard deviations and 95% confidence intervals will be calculated for MCC parameters and all secondary outcome measures. A repeated measures model will be used to compare the primary and secondary outcome measures, with the subjects considered as random factors. For hypothesis one and three, MCC values from huff-cough alone will be compared to traditional ACT methods (HFCWO-vest and OPEP) and Whole Body Vibration to test the null hypothesis that there is no difference in MCC between huff-cough and a) HFCWO-vest; b) OPEP; and c) WBV. For hypothesis two, biomarker values pre and post each ACT intervention will be compared using paired t-tests to test the null hypothesis [i.e. there is no difference between candidate biomarker concentration before and after use of a) HFCWO-vest, b) OPEP, and c) WBV]. We will also compare the change in biomarker values across different methods using a repeated measure model. Finally, we will explore the strength of the relationship between MCC responses and the corresponding change in candidate biomarker values by calculating the Spearman’s Correlation Coefficient.

Breath sounds data will be collected as a pilot project, and will not be subject to statistical measures.

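### For MCC, the primary outcome, every specified contrast is against the fixed-first huff-cough visit; the WBV-versus-device differences, the only ones with randomised order, are not specified

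*Combined protocol and SAP*

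**What the plan says.** Section 4 (Rationale for proposed study) gives as one purpose of the study to "compare a novel exercise device using whole body vibration to traditional ACT methods". The background on whole body vibration gives the reason: such a device "may be as effective in ACT as those devices that were specifically engineered to affect the respiratory system".

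On design, the Randomization section states: "Baseline (huff-cough only) measurements will be obtained at Visit 2". It continues: "For visits 3-5, a single ACT method will be employed at each visit, with a randomized order in which the methods are used". The sequence is allocated only once the control visit is over: "Subjects will be assigned to the next row in the table after the baseline visit". The Study design paragraph numbers the control visit differently, but in both places it comes before the randomised visits.

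On analysis, the primary comparison sets AUC-Clr274 under huff-cough alone against each of the three devices. The other time intervals and lung regions "will be calculated and compared in similar fashion as above". The slope analysis also compares each device with huff-cough. The model paragraph then says that MCC values will be used to "test the null hypothesis that there is no difference in MCC between huff-cough and a) HFCWO-vest; b) OPEP; and c) WBV". No difference in MCC between two devices is named.

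For other outcomes the same section does compare methods with each other: sputum weight and percent solids across the modalities, and change in biomarkers across methods in a repeated measures model.

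**The concern.** Whether WBV does as well as purpose-built devices is a device-versus-device question, and MCC is the outcome on which the study is built. The specified MCC analyses answer a different question: whether each device differs from huff-cough.

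Two things follow. First, the device-versus-huff-cough contrasts carry any effect of visit order, because huff-cough always comes first. The device-versus-device contrasts are the only ones that the Latin square protects, and for MCC the plan makes no stated use of them. Second, with no direct contrast, a reader of the results has only three separate tests against a shared control. If one device reaches significance and another does not, that is not evidence that the two differ. A contrast chosen after the data are seen would be post hoc.

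**Working it through.** **1. Which MCC contrasts are specified (Data analysis section).**

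| MCC analysis | Reference |
|---|---|
| AUC-Clr274, whole right lung (primary) | huff-cough |
| AUC-Clr over other intervals and lung regions | huff-cough, by reference to the primary |
| Change in slope, 0-16 versus 16-56 minutes | huff-cough |
| Three null hypotheses in the model paragraph | huff-cough |
| Any device versus another device | none specified |

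The model paragraph mentions a hypothesis three, but Specific Aims lists only two hypotheses. Even there, WBV is set against huff-cough.

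**2. The plan's own figure.** Inputs from the Sample size estimate: mean change 20.0, SD of change 15.1, two-sided alpha 0.05, paired t-test. dz = 20.0/15.1 = 1.325 (the plan gives 1.33). Exact noncentral-t power is 0.737 for n = 6 and 0.830 for n = 7, so the stated 7 is reproduced. With 10 subjects, power for 20 units is 0.96. All of this concerns a device against huff-cough; nothing is given for device against device.

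**3. Precision of a pairwise device difference.** The documents give no SD for this. *Assumption:* the 15.1 taken from the change after hypertonic saline also applies between two devices.

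- SE = 15.1/√10 = 4.775.
- Paired t, 9 df: 2.262 × 4.775 = **10.8** units (11.6 with 9 completers).
- Repeated measures model, 10 subjects × 4 visits, no period term since the plan names none: residual df = 40 − 1 − 9 − 3 = 27, and 2.052 × 4.775 = **9.8** units.
- Range by paired t: an SD of 10 gives ±7.2. An SD of 26.9 (19.0 × √2, the baseline SD in Table 1 with no within-subject correlation) gives ±19.2.

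By paired t with SD 15.1, 10 subjects have 80% power for a device difference of 15.0 units, which is 75% of the planned device-versus-huff-cough effect (15.0/20.0). They have 46% power for a difference of 10 units.

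**4. The optional pooled contrast.** WBV minus the mean of vest and OPEP: the residual variance is 15.1²/2 = 114.0, SE = √(114.0 × 1.5/10) = 4.14, and the half-width on 27 df is 2.052 × 4.14 = 8.5 units. The gain over 9.8 comes only from averaging two devices.

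**5. How often separate tests would mislead.** Simulation of 200,000 trials: 10 subjects, residual SD 15.1/√2 = 10.7, shared huff-cough control, two devices with the same true effect, each tested two-sided at 0.05. The table gives the share of trials in which exactly one of the two is significant.

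| True effect of both devices | Repeated measures model | Separate paired t-tests |
|---|---|---|
| 10 | 32% | 35% |
| 12 | 29% | 34% |
| 15 | 17% | 24% |
| 20 (planned) | 3% | 6% |

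The model column is the one that applies, because the plan names that model for MCC and assigns paired t-tests to the before-after biomarker comparisons.

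**The case against.** The other side has a good deal to say, and part of it stands.

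- *A reader might infer that devices are compared with huff-cough only, on every outcome.* The documents do not support that. Sputum and biomarker change are compared across modalities, and subjects are asked which method they would choose. The gap is specific to MCC.
- *A reader might infer that a stated aim has no analysis at all.* That goes too far. The sentence in section 4 names no outcome, and none of the listed hypotheses or the four Specific Aims contains a contrast of WBV with another device.
- *A reader might infer that the investigators will rank devices by which ones reach significance.* No section says so. Means, SDs and 95% CIs are planned for MCC parameters. The split rates in the working describe what happens if the results are read that way, and at the planned effect of 20 the rate is only about 3%.
- *A reader might infer that the direct contrast cannot be obtained, or that it is more precise than the planned ones.* The model can produce it; it is simply not named. Pairwise, its precision equals that of a device against huff-cough. Only the pooled contrast is tighter, and pooling could hide WBV being worse than one of the two devices.

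It can also be said that this is a pilot. That favours estimates with intervals, since section 4 gives effect size and variability as the purpose. What remains after all this is that the MCC contrasts with randomised order are not specified, although a comparison of WBV with the other devices is announced.

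**Conclusion.** The point holds for MCC. Followed as written, the plan reports three contrasts against a non-randomised first visit and leaves unspecified the device differences that its randomisation protects. This limits what the trial can say about WBV relative to vest and OPEP. It does not affect the validity of the sample size calculation for the primary comparison.

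In size: a pairwise device difference would be known to about ±9.8 units (model) or ±10.8 (paired t), and to about ±7 to ±19 by paired t over an SD of 10 to 27. Against a planned effect of 20 that is useful for estimation. It is too wide, and there is no margin, to conclude that WBV is as effective. Reading devices from separate tests would split two equal devices in about 32% of trials at 10 units, 17% at 15 and 3% at 20.

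These figures rest on 10 complete subjects, equal variance and correlation across the four visits, and an SD borrowed from the response to hypertonic saline. The absence of the MCC contrast rests on the text alone and needs none of these assumptions.

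**What to change.** In the Data analysis section, add as secondary estimation from the repeated measures model already named: the AUC-Clr274 differences WBV minus vest and WBV minus OPEP, each with a 95% CI. Vest minus OPEP, and WBV minus the mean of the two, may be added.

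State there that any remark on WBV relative to the other devices rests on these intervals and not on separate tests against huff-cough. State also that, with 10 subjects and no margin, the intervals do not establish equivalence.

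The cost is a few sentences and a few more secondary contrasts, which should be labelled as estimation. No new data or model is needed, and neither the primary comparison nor the sample size changes.

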#### **5. Experimental Design and Methods:**

**Key inclusion criteria:** Adults with confirmed diagnosis of cystic fibrosis aged 18 years and older.

**Key exclusion criteria:** Pregnant or lactating women, individuals with severe lung disease (FEV1 <30%), or with exacerbations of lung disease requiring antibiotics or medication change within four weeks prior to enrolment. Individuals unable to use vest-based HFCWO, oscillatory PEP device, or who require oxygen supplementation at rest. We will also exclude individuals with significant balance or gait impairment preventing the individual from tolerating being positioned on a vibrating platform.

**Study design:** Ten (10) adult CF subjects will be recruited from the CF clinic at UNC, and will have a screening visit and four subsequent study visits. At Study Visit 1 huff-cough alone (control) will be performed while the order of the 3 remaining airway clearance therapy (ACT) treatments received at Study Visits 3-5 will be randomized: oscillatory PEP (positive expiratory pressure), high frequency chest wall oscillatory vest, and the vibrating plate device. Only one ACT device will be used at any given visit as adjuncts to huff-coughing, with the same cough regimen used at all study visits (Figures 3 & 4). Study visits will be at least three and no more than 21 days apart. Subjects who are prescribed hypertonic saline, dornase alfa, long-acting bronchodilators, and/or airway clearance will be asked to withhold use of these agents/activities after midnight before each study visit after screening. No bronchodilators will be used as part of this study.

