**Hypothesis 1:** *Device-assisted airway clearance therapy using OPEP, HFCWO-vest, and whole-body vibration causes a demonstrable increase in MCC and expectorated sputum volume when compared to cough alone.*

**Hypothesis 2:** *Airway signaling molecules, including NO and purine nucleotides (e.g. ATP, adenosine), are associated with the regulation of MCC and mediate the increase in mucus clearance that occurs following the application of mechanical stimuli from OPEP, HFCWO-vest, and whole-body vibration.*

We will test these hypotheses through these specific aims:

**Specific Aim 1:** Measure the effects of 4 different ACT modalities on MCC, using gamma scintigraphy.

**Specific Aim 2:** Measure the effects of different ACT modalities on proposed regulators of MCC, including nucleotide levels (via exhaled breath condensate collection) and exhaled NO.

**Specific Aim 3:** Examine associations between biomarkers of airway mechanical stimulation and measured MCC.

**Specific Aim 4:** Determine what study characteristics would be needed to more fully assess the effectiveness of ACTs, including sample size, study design features, and outcome measures.

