### Study Visits

The order of procedures at each study visit is outlined in Figure 3. At each visit, subjects will be asked about intercurrent adverse events, changes in medical regimen and health status. Vital signs and a pregnancy test (if applicable) will be performed to ensure subject safety. Spirometry will not be obtained during study visits as the forced expiratory maneuver may stimulate MCC and mediator release (nitric oxide, nucleotides), and therefore may interfere with results. Exhaled breath condensate (EBC) and fraction of exhaled nitric oxide (FENO) samples will be obtained prior to the inhalation of isotope and immediately after the first ACT intervention. Procedures for biomarker collection and analysis are discussed below.

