### ***Outcome Measures***

#### *Mucociliary Clearance*

Background and transmission scans will be performed per the MCC Standard Operating Procedure (see attachment) to subtract background radiation levels and allow identification of lung boundaries and regions of interest. The Tc-99 sulphur colloid radiotracer will be inhaled using our slow inhalation, large particle method. The subject will be positioned in front of the gamma camera, and images will be obtained for 16 minutes prior to any intervention. Sixteen minutes after particle inhalation, there will be a 40-minute intervention period with whichever ACT the subject is to receive during that study visit. Following the ACT period, there will be an additional 38 minutes of image capture. After an 86-minute break (i.e. 180 minutes after tracer inhalation), an identical MCC image capture period with ACT intervention will occur (Figure 3).

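### Huff-cough alone is always the first imaging visit and only the three devices are randomised, so the primary contrasts are non-randomised and cannot be separated from a first-visit effect

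*Combined protocol and SAP*

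**What the plan says.** Section 5, Study design, fixes the control at the start: "At Study Visit 1 huff-cough alone (control) will be performed while the order of the 3 remaining airway clearance therapy (ACT) treatments received" over the remaining visits is randomised. The Randomization section gives a different visit number, "Baseline (huff-cough only) measurements will be obtained at Visit 2", which agrees if screening counts as Visit 1. On either numbering the control is the first imaging visit, because the Screening Visit lists examination, history, medication review and spirometry but no clearance scan. The devices are then ordered over visits 3–5 by a 3x3 Latin square: "Subjects will be assigned to the next row in the table after the baseline visit". The reason given for waiting is to confirm eligibility first.

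Hypothesis 1 is causal: each device "causes a demonstrable increase in MCC and expectorated sputum volume when compared to cough alone". The primary comparison under Data analysis is AUC-Clr274 under huff-cough against each of vest, OPEP and WBV. The analysis is a repeated measures model with subject as a random factor, and no visit or period term is named. A secondary analysis uses the change in clearance slope from 0–16 to 16–56 minutes, which "will be used to compare the immediate effects of each ACT versus. huff coughs alone".

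**The concern.** What is randomised and what is tested do not match. Device order is balanced, but no subject has the control anywhere except first. The difference between a device and huff-cough is therefore the device effect plus whatever changed after the first imaging visit. Candidates are practice at the slow tracer inhalation, practice at the huff-cough routine, and drift in health over a gap of 9 to 63 days between the control and the last device visit (three intervals of 3 to 21 days).

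An upward shift mimics benefit and a downward shift hides it. Because the same control scan enters all three contrasts, agreement among the devices would not be reassuring. Sections 3 and 4 say the pilot is meant to determine effect sizes and inform the design of later trials, so the bias falls on the quantity the study exists to estimate.

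**Working it through.** **Inputs.** From the Sample size estimate: effect 20.0 units, SD of paired change 15.1, two-sided α = 0.05, 10 subjects. From Table 1: interpolated baseline 32.4. From section 5: four imaging visits. The size of any visit shift δ is not in the documents and is assumed below.

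**1. The plan's own figure.** dz = 20.0/15.1 = 1.32 (the plan prints 1.33). Paired-t power is P(|T| > t(0.975, n−1)) for a noncentral t with n−1 df and noncentrality dz·√n. With dz = 1.33, n = 6 gives 74% and n = 7 gives 83.3%, so the stated 7 is reproduced. At n = 10, using 20.0/15.1, power is 96.0%. The sample size is not the problem, and more subjects would not remove the bias.

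**2. Estimability in the planned order.** Fixed-effects design matrix for 10 subjects × 4 visits (40 rows):

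| Model | Columns | Rank | Variance of device − huff-cough |
|---|---|---|---|
| subject + condition | 13 | 13 | 2/10 = 0.200 σ² |
| + visit as 4 categories | 16 | 15 | not estimable |
| + linear visit | 14 | 14 | 0.382, 0.402, 0.423 σ² |

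The huff-cough indicator equals the first-visit indicator, which accounts for the missing rank. All device-against-device contrasts remain estimable. The linear model works only by extrapolating a trend from visits 3–5 back to the control visit, which these data cannot test. With σ = 15.1/√2 = 10.68 (equal SD of every pairwise difference assumed), its power for 20 units is 79–83%, against 98.1% without the term.

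**3. Effect of a shift δ.** For the paired t, the noncentrality with no device effect is (δ/15.1)·√10 on 9 df. With a true 20 units and a downward shift it is ((20−δ)/15.1)·√10. For the repeated measures model, SE = 10.68·√0.200 = 4.78 on 27 df.

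| δ (units) | δ/32.4 | Rejection, no device effect: paired t | same: repeated measures | Power for true 20, downward δ: paired t |
|---|---|---|---|---|
| 0 | 0% | 5% | 5% | 96.0% |
| 2.5 | 8% | 7.6% | 8.0% | 90.2% |
| 5 | 15% | 15.5% | 17.3% | 79.8% |
| 10 | 31% | 46.4% | 52.4% | 46.4% |

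Rejection rates are the same for upward and downward shifts. By simulation with paired t-tests, the chance that at least one of the three comparisons is significant with no device effect is about 13% with no shift, 33% at 5 units and 73% at 10 units.

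**4. The alternative.** A 4x4 Williams square over the same four visits with 10 subjects and categorical visit has rank 16 of 16. Contrast variances are 0.202–0.204 σ², SE 4.80–4.82 against 4.78 now, on 24 df. Power for 20 units is 97.8–97.9%.

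**5. Lost controls under the alternative.** In examples where only the huff-cough scan is missing, the variance is 0.22–0.23 σ² for one subject (power at least 96%) and 0.25–0.26 σ² for two (at least 93%). If those subjects also miss every later visit, the same matrices with those rows deleted give 0.22–0.24 σ² for one subject and 0.24–0.30 σ² for two, with power at least 95% and 90%.

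**The case against.** The fixed order is stated openly. Huff-cough is called a baseline, a reason is given for late assignment, and this is a 10-subject pilot. No document shows a first-visit effect. The manoeuvre is coached by instruction, the same cough regimen is used at every visit, and imaging follows a standard procedure. The order also has benefits: every analysed subject has a control scan, and no study device precedes it.

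Some of this stands. The shifts are illustrative. The percentages use the baseline of the hypertonic saline data, and the plan expects its own control to be accelerated by huff-cough, so the same shifts would be smaller percentages of it. The SD of 15.1 comes from the same saline data. The within-visit slope contrast is less exposed to between-visit shifts. The plan also contains a partial check, since "images will be obtained for 16 minutes prior to any intervention". That check cannot reveal learned huff-cough technique, because no huff-cough takes place before minute 16.

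The eligibility reason has some basis: pregnancy is an exclusion, and the only pregnancy test described is at study visits ("Vital signs and a pregnancy test (if applicable) will be performed to ensure subject safety"). That these checks precede imaging is an inference, because the flow figure is not shown, but it is the natural reading. Eligibility can then be confirmed before assignment to any of four conditions, so the control need not come first.

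Carryover is no argument for the current order. If every device left a 5-unit carryover into the next visit, the planned contrasts would be biased by +3.0 to +3.5 units and the Williams contrasts by −0.8 to −1.5.

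**Conclusion.** The concern holds. The three primary contrasts are non-randomised and fully aliased with any first-visit effect, and no planned or available visit term repairs this without an untestable assumption and about twice the variance. The aliasing follows from the visit order alone. Its practical size is unknown: it would be minor at 2.5 units, but at 10 units, half the planned effect, a device with no effect would test significant in about half of such trials. Those figures assume an SD of change of 15.1, 10 complete subjects and α = 0.05 per comparison. Comparisons among the three devices are protected by the randomisation.

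**What to change.** Make huff-cough a fourth condition in a 4x4 Williams square over the same four visits: four sequences, each condition once per visit and following every other condition once. Assign the sequence at the first imaging visit, after the pregnancy test, health status and medication checks and before anything that depends on the condition. Fit condition and visit as fixed effects with subject random. The visit term is needed because 10 is not a multiple of 4. Reword the Missing Data/Subject Drop Out rule so that it does not presume the control comes first, and reconcile the visit numbering between the Study design and Randomization text.

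The cost is an amended randomisation table, model sentence and replacement rule, with no extra visits, scans or subjects. There are three downsides:

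- A subject who leaves before the huff-cough visit has no within-subject control, and the plan's 10% bounds only drop-out beyond visit 3.
- A device visit may precede the control by as little as 3 days, a gap already accepted between devices.
- Ten subjects split 3/3/2/2 over four sequences instead of 4/3/3 over three.

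The square removes additive visit effects only.

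If the order is kept, state that the primary comparison is a non-randomised before-after comparison, and report the 0–16 minute clearance slope at the control visit against visits 3–5 as a partial check for a visit shift.
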